5.2. Sample Size Sensitivity

The sample size and power calculations are based on assumptions about the true values for parameters. The power of the study is dependent on changes in these assumptions, in particular the assumed annualised exacerbation rates. Table 7 illustrates how changes in assumptions for two parameters (placebo + SoC annualised exacerbation rate and treatment effect) affect the power.

Table 7Estimates of Power for Assumed Placebo + SoC Exacerbation Rate
and Assumed Percent Reduction with GSK3511294 + SoC Compared
with Placebo + SoC

Percent reduction in annualised	Placebo + SoC annualised exacerbation rate				
exacerbation rate with GSK3511294 + SoC vs. placebo + SoC	1.0	1.1	1.18	1.3	
30%	61	63	65	67	
40%	88	90	91	92	
50%	98	99	99	99	

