4.11.2. Unblinded Interim Analysis for Futility

An unblinded interim analysis for futility will be conducted by an independent SDAC in conjunction with an IDMC to maintain study integrity.

The futility analysis will evaluate efficacy based on the primary endpoint of annualised rate of clinically significant exacerbations using interim data from Phase III studies 206713 and 213744 (this study) when approximately 675 participants are randomised across both studies. The stopping rule is binding, i.e. if the stopping criteria is met then the recommendation will be to stop, conditional on the IDMC deeming that there is no delayed onset of clinical efficacy. Should it be judged that there is delayed onset then this may invalidate an assumption of the interim analysis that the pre-interim data is reflective of post-interim data which could result in inflation of type 2 error. In such a situation, the IDMC will use their expert judgment in determining their recommendation.

Recruitment into the study will continue whilst the futility analysis is taking place. Any communication to the sites regarding the decision will only take place if a decision to stop the study is made. Should the studies be stopped, all on-going participants will complete their follow-up period but will not receive any further doses whilst no further participants will be recruited into the study.

The full details of the process are included in IDMC Charter.

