4.11.2.1. Decision Rule

The interim analysis will be based on the predictive probability of meeting the end of study (program) success criteria (defined as statistical significance at a two-sided 5% alpha level in **both** studies 206713 and 213744). Should the predictive probability of success be less than or equal to 0.25 then the studies will be stopped for futility.

The futility rule:

Futility	Continue
Predictive probability (statistical	Predictive probability (statistical
significance two-sided 5%) in both	significance two-sided 5%) in both 206713
$206713 \& 213744) \le 0.25$	& 213744) > 0.25

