 - 1. The design matrix (Z) is multiplied with the set of posterior β samples and then back-transformed (exponentiated) to give expected annualised

exacerbation rate for each participant (μ_i) based on the interim data. Note: for participants yet to be randomised, and therefore without values observed for baseline covariates, bootstrapping from already randomised participants will be performed.

- 2. The expected exacerbation rate for the pre-interim and post-interim periods are calculated by multiplying μ_i by the pre-interim and post-interim times in the study for the participant: $\hat{y}_{i,1} = \mu_i \times t_{i,1}$ and $\hat{y}_{i,2} = \mu_i \times t_{i,2}$.
- 3. For the two periods (pre and post-interim), the number of exacerbations within each period is negative binomial. The distribution of one period conditional upon the other, within a participant, is also negative binomial [Keene, 2014]. The negative binomial parameters for the post-interim period are calculated for each participant and set of posteriors samples (iteration):

$$p_{i,2} = \frac{\frac{1}{k} + \hat{y}_{i,1}}{\frac{1}{k} + \hat{y}_{i,1} + \hat{y}_{i,2}}$$
$$k_{i,2} = k_1 + count_{i,1}$$

Where k_1 is the sampled dispersion parameter, $count_{i,1}$ is the number of exacerbations for participant *i* in period 1 (pre-interim), *i* is the participant and j=1,2 is the period (pre, post-interim).

Using these parameters, simulate a participant's number of clinically significant exacerbations for post-interim data for each set of posterior samples

- 4. The pre-interim observed data (one set) will be combined with each set of postinterim data (1000s of sets) to create 1000s of end of study datasets
 - 1. Each participant's exacerbation count will be the summation of pre-interim observed count (if the participant was randomised at least one month before the interim data cut) plus the post-interim simulated exacerbation count (if the participant did not complete before the interim).
 - 2. Each participant's length of time in the study will now be the assumed average length of time in the study, which is set at 0.86 years.
- 5. The primary analysis model is applied to each iteration (dataset), each study separately. The p-value for the treatment effect (rate ratio) will be calculated. For each iteration, if the success criteria (statistical significance at 5% two-sided level for both studies) is met then the iteration is marked as success (flag as 1), or if not then fail (flag as 0).

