4.11.2.3. Timing and Operating Characteristics

The proposed timing of the futility analysis is when approximately 675 participants have been randomised across the studies. At this time it is estimated that approximately 200 participants will have completed the studies and 500 received both doses (i.e. at least 6 months worth of data). The median follow-up time in the interim analysis is estimated to be 9 months with the information fraction for the primary endpoint estimated to be 60%, where information fraction is calculated as:

$$Information \ fraction = \frac{\sum_{i=1}^{n(interim)} length \ of \ time \ in \ study \ at \ interim_i}{\sum_{i=1}^{750} length \ of \ time \ expected \ in \ complete \ study_i}$$

Table 5 shows operating characteristics of the futility analysis for a range assumed true treatment effects when approximately 725 participants have been randomised (proposed interim timing). Operating characteristics were obtained by simulating 5,000 studies and following the steps in Section 4.11.2.2 for each simulated study. Operating characteristics are obtained from the aggregate of these simulations.

As this is a futility analysis and there is no opportunity to stop for efficacy the type 1 error (calculated under the null hypothesis of assumed rate ratio = 1) is controlled well below the 5% level. The power of each study is approximately 99%, compared with >99% in the scenario where there is no futility analysis (as described in the protocol). The

expected observed rate ratio at the interim to trigger futility is expected to be approximately 0.70.

Assumed treatment effect (rate ratio depemokimab vs. placebo)	Probability of success (statistical significance in both studies)	Power ¹ : 206713	Power1: 213744	Probability of futility
1	<0.01	<0.01	<0.01	0.98
0.9	0.01	0.04	0.02	0.94
0.8	0.08	0.18	0.13	0.76
0.7	0.37	0.50	0.44	0.42
0.6	0.78	0.85	0.82	0.11
0.5	0.98	0.98	0.98	0.01

Table 5 Operating Characteristics of Futility Analysis

¹ at two-sided 5% significance level for end of study test and incorporating the possibility of futility

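### SAP Section 5 gives power without the interim and does not say so; under the binding futility stop, power falls from 65% to about 49% at a 30% reduction and from 91% to about 85% at 40%

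*SAP*

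**What the plan says.** **Power.** SAP 5.1.1 states 99% power for 250 versus 125 participants at a placebo rate of 1.18 and a 50% reduction, with dispersion 0.8 and 14% of participant-years missing. SAP 5.2 then varies the inputs: "Table 7 illustrates how changes in assumptions for two parameters (placebo + SoC annualised exacerbation rate and treatment effect) affect the power". At rate 1.18, Table 7 gives 65, 91 and 99% for 30, 40 and 50% reductions. Protocol Table 4 prints the same values. Nothing in SAP Section 5 mentions an interim.

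**Interim.** SAP 4.11.2 plans one unblinded futility look, pooled with study 206713, "when approximately 675 participants are randomised across both studies". On its status: "The stopping rule is binding, i.e. if the stopping criteria is met then the recommendation will be to stop". The same sentence attaches a condition that rests on the committee's judgement: "conditional on the IDMC deeming that there is no delayed onset of clinical efficacy". SAP 4.11.2.1 sets the threshold: "Should the predictive probability of success be less than or equal to 0.25 then the studies will be stopped for futility". Success there means two-sided 5% significance in both studies. SAP 4.11.2.2 uses "the assumed average length of time in the study, which is set at 0.86 years". SAP 4.11.2.3 has "the information fraction for the primary endpoint estimated to be 60" per cent.

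**Power with the interim.** SAP Table 5 is footnoted "at two-sided 5% significance level for end of study test and incorporating the possibility of futility". For this study (213744) it prints 0.44, 0.82 and 0.98 at rate ratios 0.7, 0.6 and 0.5, with futility probabilities of 0.42, 0.11 and 0.01.

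**Timing.** SAP 4.11.2.3 opens with about 675 randomised as the proposed timing. It then introduces Table 5 at about 725 randomised and labels that the proposed timing as well.

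**The concern.** Section 5.2 is where a reader looks to see how the study fares if the drug works less well than hoped. That reader would take this study to have 65% power at a 30% reduction and 91% at 40%. Elsewhere the same SAP prints 44% and 82% for the same study and the same effects. The two sets differ because one leaves out a stopping rule that the plan adopts, and Section 5 neither says this nor refers to Table 5.

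What is at stake is the reader's picture of robustness at weaker effects. The test, its type I error and the case for the sample size at the design effect are not affected.

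The timing conflict matters for a different reason. A binding rule needs one planned look, with operating characteristics computed at that look. As written, Table 5 is described at a different size from the one in SAP 4.11.2.

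**Working it through.** **Inputs.** n = 125 and 250; two-sided 5%; placebo rate r0 = 1.18; dispersion k = 0.8 (SAP 5, 5.1.1). Mean follow-up t = 1 − 0.14 = 0.86 years, which agrees with SAP 4.11.2.2.

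**Step 1: reproduce Table 7 with no interim.** Wald test on the log rate ratio, with r1 = RR × r0:

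V = (1/(r0·t) + k)/125 + (1/(r1·t) + k)/250; power = Φ(|ln RR|/√V − 1.96).

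At RR 0.7, r0·t = 1.0148 and r1·t = 0.7104. So V = (0.9854 + 0.8)/125 + (1.4077 + 0.8)/250 = 0.01428 + 0.00883 = 0.02311, and √V = 0.1520. Power = Φ(0.3567/0.1520 − 1.96) = Φ(0.386) = 65.0%.

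| Placebo rate | 1.0 | 1.1 | 1.18 | 1.3 |
|---|---|---|---|---|
| RR 0.7: computed (Table 7) | 60.7 (61) | 63.2 (63) | 65.0 (65) | 67.4 (67) |
| RR 0.6: computed (Table 7) | 87.9 (88) | 89.7 (90) | 90.9 (91) | 92.4 (92) |
| RR 0.5: computed (Table 7) | 98.5 (98) | 98.9 (99) | 99.2 (99) | 99.4 (99) |

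All 12 cells agree within a point, so Table 7 is power without the interim.

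**Step 2: add the stop.** This is a normal approximation to the predictive-probability rule, for two replicate studies with information fraction f = 0.6 in each:

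- Interim estimate in study j: e_j ~ N(ln RR, V/0.6). Final estimate = 0.6·e_j + 0.4 × (independent estimate from the remaining information).
- Effect used for prediction: pooled, θ ~ N((e_1 + e_2)/2, V/1.2).
- Stop both studies if the predicted probability that both final estimates are below −1.96√V is 0.25 or less. Significance counts only if there was no stop.

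Results from 200,000 simulated programmes per cell (Monte Carlo error about 0.1 point), r0 = 1.18:

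| Reduction | Power, no interim | P(stop) | Power with stop | Loss | SAP Table 5, this study |
|---|---|---|---|---|---|
| 30% | 65.0 | 38.2 | 48.7 | 16.3 | 44 |
| 40% | 90.9 | 9.6 | 84.8 | 6.1 | 82 |
| 50% | 99.2 | 0.8 | 98.5 | 0.7 | 98 |

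**Step 3: sensitivity.** With equal information anywhere from 50% to 70%, power with the stop is about 48–49, 84–85 and 98–99%. Across Table 7's placebo rates 1.0, 1.1, 1.18 and 1.3 it is 43.8, 46.5, 48.7 and 51.8% at a 30% reduction, and 80.1, 82.8, 84.8 and 87.1% at 40%. No tested rate brings back the printed value.

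**Step 4: the remainder against Table 5.** 48.7 − 44 = 4.7 points at 30% and 84.8 − 82 = 2.8 points at 40%. Table 5 does not state its placebo rate, dispersion or accrual by study. It also gives the two studies 0.50 and 0.44 at RR 0.7. With 5,000 simulations the standard error of that difference, treating the columns as independent, is √((0.50·0.50 + 0.44·0.56)/5000) = 0.010. The gap is therefore 6 standard errors, and the studies must have had different settings. Slower recruitment here is one possibility. With assumed information of 70% and 50%, the less advanced study has 46.7 and 83.9% power at 30 and 40% reductions; with 80% and 40%, it has 44.9 and 83.4%.

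**Step 5: 675 versus 725.** Assume uniform accrual of 750, no withdrawal, and inclusion after one month.

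- 750 over 1.6 years is 469 a year, so 675 is reached at 1.44 years. Completed: 469 × 0.44 ≈ 207. Median follow-up about 9.2 months. Information: 469 × (0.5 + 0.44)/750 ≈ 0.59.
- 750 over 1.45 years is 517 a year, so 725 is reached at 1.40 years. Completed: 517 × 0.40 ≈ 208. Median about 8.9 months. Information: 517 × (0.5 + 0.40)/750 ≈ 0.62.

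SAP 4.11.2.3 describes about 200 completed, 9 months and 60%. Either size fits those three figures, so they do not show which one Table 5 used. Between 0.59 and 0.62 information, power with the stop changes by under 0.5 point.

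**The case against.** The strongest reply is that nothing here is miscalculated. Table 7 is right for what it computes, and its introductory sentence claims only to vary two parameters. Protocol 9.6 sends the interim's operating characteristics to the SAP or charter, and SAP 4.11.2.3 supplies them at six effect sizes, footnoted as including futility. It even identifies the protocol's power as the case with no futility analysis. Stopping at weak effects is what the rule is for, and the stop depends on the IDMC's view of delayed onset.

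Much of this stands. The fault is a missing label, not wrong arithmetic. But SAP 4.11.2.3 draws the comparison in words only at the design effect, where the loss is under 1 point. Table 7 exists to show what happens away from that effect, where the loss is 6 to 16 points and Section 5 is silent.

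A reader might go further in three ways that the documents do not support:

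- **Assigning all of the 9- and 21-point gaps between Tables 7 and 5 to the stop.** Table 5's inputs are unstated, so only about 6 and 16 points can be traced to it.
- **Using Table 5's futility probability of 0.42 to cap power at 58% in every column of Table 7's 30% row.** That probability belongs to one unstated placebo rate. In the approximation above, the stop probability at RR 0.7 runs from about 42.5% at rate 1.0 to 35.3% at 1.3.
- **Treating the text's approximate 99% as contradicting Table 5's 0.98.** A value near 98.5% is fairly described by either.

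**Conclusion.** The point holds as one of labelling and reconciliation. Table 7 and the 99% in SAP 5.1.1 exclude a stop that the plan adopts, and Section 5 does not say so. With the stop applied strictly, this study's power is about 49% rather than 65% at a 30% reduction, about 85% rather than 91% at 40%, and about 98.5% rather than 99.2% at 50%. This rests on the SAP's stated inputs, 60% information in both studies and a normal approximation to the Bayesian rule. If the IDMC sets the rule aside for delayed onset, the loss is smaller.

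A reader might infer that the study is underpowered. The documents do not support that: at the effect the study was sized for, the loss is under 1 point. Nor can SAP 1.2 be faulted for repeating the 99%, because its Interim Analysis row is blank in the available text and may already carry the caveat.

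The 675/725 conflict is plain on the page, but it moves power by under about 0.5 point.

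**What to change.** - Label Table 7 and the 99% in SAP 5.1.1 as power without the interim.
- Reconcile 675 and 725 in SAP 4.11.2 and 4.11.2.3.
- State the interim size, placebo rate, dispersion and accrual by study used for Table 5. Re-run it only if it was not computed at the size actually used.
- Once Table 5 is confirmed, cross-refer to it from SAP 5.2. Note that it assumes strict application of a rule that depends on the IDMC finding no delayed onset.

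The cost is a few lines of SAP text and at most one re-run of existing simulation code. Sample size, alpha, stopping rule and analysis do not change.

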5.3. Sample Size Re-estimation or Adjustment

There will be no sample size re-estimation.

There is a possibility for randomising greater than 375 participants in the study. This is due to local country requests or requirements, for example, the local health authority specifying a minimum number to be enrolled. The primary analysis and clinical study report (CSR) will be based on the initial target enrolment. If the study target enrolment is reached before a local country enrolment requirement is met, then recruitment in that country may continue. Participants from those countries, who have already been enrolled at the time of reaching the target enrolment, will be included in the primary analysis. All data (pre- and post-target enrolment) will be analysed together but reported later in a supplement to the study report. Inferences will be drawn on the original study report based on the target enrolment.

6. SUPPORTING DOCUMENTATION

6.1. Early PK Access Key Activities

Designated representative(s) may be unblinded for performing population PK, PKPD dataset preparation and draft PK, PKPD model development using scrambled (random reassignment of subject identification numbers) PK, PKPD unblinded datasets. The PK and PKPD datasets will include information on PK concentration, actual dosing information, demographics (including race and ethnicity), vital signs, concomitant medications, antidrug antibodies, biomarkers (e.g. eosinophils and IL5 concentration) and laboratory information. No information on adverse event and efficacy will be included.

6.2. Appendix 1 Abbreviations and Trademarks

6.2.1. List of Abbreviations

Abbreviation	Description	
ACQ	Asthma Control Questionnaire	
ADA	Anti-drug antibody	
ADSD	Asthma Daily Symptom Diary	
AE	Adverse Event	
AESI	Adverse Event of Special Interest	
ANSD	Asthma Nightly Symptom Diary	
Anti-IL-5	Anti-Interleukin-5	
ВР	Blood pressure	
CI	Confidence interval	
COVID-19	Coronavirus disease 2019	
CPMS	Clinical Pharmacology Modeling and Simulation	
CSR	Clinical Study Report	
ECG	Electrocardiogram	
eCRF	Electronic Case report form	
ED	Emergency Department	
eDiary	Electronic diary	
FAS	Full Analysis Set	
FAS	Full Analysis Set	
FEV1	Forced expiratory volume in 1 second	
GSK	GlaxoSmithKline	
HRQoL	health-related quality of life	
ICS	Inhaled corticosteroids	

Abbreviation	Description	
IDMC	Independent Data Monitoring Committee	
IgE	Immunoglobulin E	
IL-5	Interleukin-5	
IM	Intramuscular	
IV	Intravenous	
KR method	Kenward and Roger method	
LOS	Length of Stay	
LS Mean	Adjusted mean for the treatment group	
LS Mean Change	Adjusted mean change from baseline for the treatment group	
MAR	Missing at Random	
Max	Maximum	
MedDRA	Medicinal dictionary for regulatory activities	
Mg	Milligram	
Min	Minimum	
MMRM	Mixed Models Repeated Measures	
MNAR	Missing Not at Random	
NAb	Neutralising antibody	
NHANES	National Health and Nutrition Examination Survey	
OCS	Oral corticosteroids	
OPS	Output and Programming Specification	
OR	Odds ratio	
PD	Pharmacodynamics	
PEF	Peak expiratory flow	

Abbreviation	Description	
PGI-C	Patient Global Impression of Change	
PGI-S	Patient Global Impression of Severity	
РК	Pharmacokinetics	
PRO	Patient-reported outcomes	
PROMIS	Patient-reported outcomes measurement information system	
PT	Preferred Term	
QTcF	QTc corrected by Fridericia's formula	
RAP	Reporting and Analysis Plan	
SAC	Statistical Analysis Complete	
SAE	Serious adverse event	
SAP	Statistical Analysis Plan	
SC	Subcutaneous	
SD	Standard Deviation	
SE	Standard Error	
SGRQ	St George's Respiratory Questionnaire	
SNOT-22	Sino-nasal Outcomes Test-22	
SoC	Standard of care	
SOC	System Organ Class	

